5.5 Availability

Both tramadol and buprenorphine are FDA approved and commercially available

5.6 Usage of Concurrent/Concomitant Medications

Use of all the medications mentioned below are allowed

- Antidiarrheal like loperamide and Lomotil (atropine and diphenoxylate).
- Antiemetics like prochlorperazine, steroids or serotonin antagonists may be used if clinically indicated.
- Antihistamines.
- Topical steroid creams.
- Anticoagulants.
- Viscous lidocaine.
- NSAIDS before starting study regimen.
- Tylenol® before starting study drug regimen or any time for fever.

CYP3A4 inhibitors and inducers: Buprenorphine is mainly a substrate of CYP3A4, and the manufacturers and others advise caution in its concurrent use with CYP3A4 inhibitors (e.g., cimetidine, clarithromycin, erythromycin, itraconazole, ketoconazole, protease inhibitors), because it may cause decreased clearance of buprenorphine, which could lead to an increase in buprenorphine plasma concentrations and result in increased or prolonged opioid effects. If coadministration with TD buprenorphine is necessary, monitor patients for respiratory depression and sedation at frequent intervals and consider dose adjustments until stable drug effects are achieved. Similarly, CYP3A4 inducers (e.g., carbamazepine, phenobarbital, phenytoin, rifampin) could reduce buprenorphine levels. These agents should be avoided during treatment with study regimen. If coadministration or discontinuation of a CYP3A4 inducer with TD buprenorphine is necessary, monitor for signs of opioid withdrawal and consider dose adjustments until stable drug effects are achieved.

Anticholinergics: Anticholinergics or other drugs with anticholinergic activity when used concurrently with opioid analgesics may result in increased risk of urinary retention and/or severe constipation. Monitor patients for signs of urinary retention or reduced gastric motility when TD buprenorphine is used concurrently with anticholinergic drugs.

5.7 Prohibited Medications

Alcohol, and use of other opioids, such as fentanyl or morphine or hydromorphone will not be allowed with study drug regimen. CNS depressants, such as benzodiazepines, antidepressants, antipsychotics should be used with caution as concurrent use of these agents with any opioids including buprenorphine can increase the risk of respiratory depression, profound sedation and in rare cases even coma and death.

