2. HYPOTHESIS, OBJECTIVES, AND ENDPOINTS

We hypothesize that the use of long-acting transdermal buprenorphine (FDA-approved dose from 5 mcg to 20 mcg/week) in conjunction with oral tramadol (50 mg to 400 mg/day) as needed for breakthrough pain will lead to a significant reduction in mucositis-related pain in locally advanced head and neck cancer patients being treated with radiation therapy by the end of treatment and the follow-up period of nine weeks.

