11. Patients presenting with any other cause of pain not related to radiation-induced mucositis or head and neck cancer, VAS >4/10 on BPI questionnaire (question 3: worst pain in last 24 hours) on the day of enrollment requiring opioid medications for pain control
12. Patients with a history of myocardial infarction ≤ 6 months prior to registration.
13. Patients with a history of significant respiratory depression; acute or severe bronchial asthma; known or suspected gastrointestinal obstruction, including paralytic ileus.
14. History of serious or severe hypersensitivity reaction to buprenorphine, tramadol or any of its excipients.
15. Use of the following drugs will not be permitted after initiation of study drug regimen: capsaicin, NSAIDS, tetrahydrocannabinol, and cannabinoids. Refer to Section 7 for details on contraindication of drug regimen. Patients will be allowed to participate in the study if they have been using antidepressants like SSRI'S, other antipsychotics and antiseizure medications for at least 4 weeks prior to enrollment on the study. Chronic use of these agents will not affect our primary endpoint of assessing impact of study regimen of Buprenorphine and Tramadol on alleviating acute radiation induced mucositis pain. As per package insert of buprenorphine and tramadol concomitant use of the above-mentioned agents with study pain regimen is not contraindicated. However, clinicians are advised to exercise caution as there have been some rare incidences of serotonin release syndrome (SRS) with concurrent administration of SSRI's and Tramadol. Buprenorphine is also not contraindicated but should be used with caution in patients with h/o seizure disorders. Study regimen can be stopped if SRS or any other adverse event occurs as a consequence of this combination. Periodic EKG's will also be performed to monitor for QTc prolongation.
16. Pregnant and lactating women are excluded from this study because chemotherapy and radiation given for the treatment of HNSCC have a potential for teratogenic or abortifacient effects. Additionally, buprenorphine is classified as category C for use during pregnancy, which means that the risk of adverse effects on the fetus cannot be ruled out. Buprenorphine does cross the placenta, and the use of opioids during pregnancy may result in neonatal withdrawals soon after birth. Symptoms of this may include irritability, apnea, increased tone, tremor, convulsions, or respiratory depression

Subject Initials: _____

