4.11 Discontinuation of Study Treatment, Withdrawal, and Compliance

Discontinuation from the study treatment does not mean discontinuation from the study. The subject will be considered in follow-up, study procedures should still be completed as indicated by the study protocol, and AEs/SAEs will continue to be reported according to this protocol.

In the absence of treatment delays due to adverse events, study treatment/intervention may continue until:

- General or specific changes in the subject's condition renders the subject unacceptable for further treatment in the investigator's judgment.
- An inter-current illness that prevents further treatment administration.
- The subject decides to withdraw from the study.
- The subject has significant noncompliance with the protocol (see below).
- Unacceptable adverse event(s) and/or dose level reduction beyond requirements as detailed in this protocol.
- The clinical need for concomitant therapy that is not permitted in the study.
- Subjects who sign the informed consent form, enroll, and receive the study intervention, but subsequently withdraw, or are withdrawn or discontinued from the study will not be replaced.

Consent Withdrawal

A subject may decide to withdraw from the study at any time. MCWCC CTO will follow their IRB of record's SOPs regarding consent withdrawal.

If a subject intends on withdrawing consent, staff should confirm which of the following options the subject chooses and document the discussion:

- Full consent withdrawal, with no study follow-up.
- Selective consent withdrawal from the interventional portion of the study but agree to continued follow-up of associated clinical outcome information.

Investigator-initiated Withdrawal

The investigator will withdraw a subject whenever continued participation is no longer in the subject's best interests. Reasons for withdrawing a subject include, but are not limited to, disease progression, the occurrence of an adverse event or a concurrent illness, a subject's request to end participation, a subject's noncompliance, or simply significant uncertainty on the part of the investigator that continued participation is prudent. The reason for study withdrawal and the date the subject was removed from the study must be documented.

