The OM Pain App will be installed on their smartphone. Subjects who do not have a smartphone will be provided with a wifi-enabled device with a pre-installed OM Pain App. Treatment with the study regimen will commence once at least grade 1 radiation-related mucositis is observed and mucositis-related pain measured by the visual analog scale (VAS) on BPI questionnaire $\geq (4/10)$ anytime during radiation therapy. Pain scores will be evaluated according to the visual analog scale (VAS), with 0 indicating no pain, 10 indicating the worst pain, 1–3 indicating mild pain, 4–6 indicating moderate pain, and scores ≥ 7 indicating severe pain. Investigators in earlier studies on radiation-induced mucositis pain have used Tylenol®, NSAIDS, and viscous lidocaine to manage mild pain and initiated long-acting pain medications like buprenorphine and fentanyl patch to treat moderate to severe pain. For the study purposes, we decided to start the treatment regimen once radiation mucositis pain $> 4/10$ VAS pain score on the BPI and pain app. The study drug combination, including transdermal buprenorphine 5 mcg to 20 mcg/week with oral tramadol 50 mg to 400 mg/day as needed for breakthrough pain (details in Table 2), will be provided to the study population. Drug will be dispensed by investigators after verifying opioid use information on WIPDMP. Radiation-induced mucositis begins to heal approximately two weeks after the last dose of stomatotoxic chemotherapy or radiation therapy.(30, 32) We will assess a percentage decrease in pain score by the end of week 9 of treatment to show a drug response. This way, we will try to avoid any bias of the normal healing process on pain alleviation. Based on our clinical practice experience and earlier studies, most HN patients will continue to have moderate to severe mucositis pain until 12 weeks of the follow-up period. Thus, we decided to monitor these patients for 12 weeks in our study.(32) Moreover, it would be easier to focus on the side effect profile of the study drug combination after completion of radiation therapy, as both chemotherapy and radiation may confound adverse event assessment of study drug regimen.

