7.1.4 Contraindications

The only true contraindication to buprenorphine use is a hypersensitivity reaction to it. Its use requires caution in patients with respiratory depression, seizure disorder, and gastrointestinal obstruction. It should be avoided in patients with gastrointestinal obstruction and surgical abdomen, such as pancreatitis or appendicitis. Patients with significant respiratory depression, such as severe chronic COPD, asthma, or myasthenia gravis should not be given buprenorphine. Buprenorphine is also not a recommended agent for patients who are currently using full opioid agonists, such as heroin or morphine, because the concurrent use of a full and partial agonist may result in acute withdrawal (see "Monitoring"), thus, defeating the purpose of buprenorphine administration. Concurrent use of benzodiazepines, other CNS depressants and alcohol is prohibited. (42)

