7.2.4 Contraindications

- Patients who have previously demonstrated hypersensitivity to tramadol, any other component of this product or opioids.
- GI obstruction, surgical abdomen like pancreatitis or appendicitis.
- Patients with significant respiratory depression like severe chronic COPD/asthma or myasthenia gravis.
- Patients with acute or severe bronchial asthma or hypercapnia in unmonitored settings or the absence of resuscitative equipment.
- It also decreases seizure threshold by antagonizing 5HTc receptors.(47)
- All other opioid contraindications, including intoxication with alcohol, hypnotics, narcotics, centrally acting analgesics, opioids or psychotropic drugs.

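### Section 5.7 allows benzodiazepines and other CNS depressants with caution, while section 7.1.4 prohibits them, and nothing in the protocol says which rule governs

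*Combined protocol and SAP*

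**What the plan says.** Four places in the combined protocol and SAP deal with CNS-active drugs taken alongside the study regimen.

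- **Section 5.7 (Prohibited Medications)** disallows alcohol and other opioids. It then says "CNS depressants, such as benzodiazepines, antidepressants, antipsychotics should be used with caution", and warns of respiratory depression, deep sedation and, rarely, coma or death.
- **Section 7.1.4 (buprenorphine contraindications)** says "Concurrent use of benzodiazepines, other CNS depressants and alcohol is prohibited".
- **Section 4.10, exclusion 15** says "Use of the following drugs will not be permitted after initiation of study drug regimen: capsaicin, NSAIDS, tetrahydrocannabinol, and cannabinoids". It refers the reader to Section 7 for contraindications. It also admits patients "if they have been using antidepressants like SSRI'S, other antipsychotics and antiseizure medications for at least 4 weeks prior to enrollment", and describes those agents as not contraindicated.
- **Section 7.2.4 (tramadol contraindications)** lists "All other opioid contraindications, including intoxication with alcohol, hypnotics, narcotics, centrally acting analgesics, opioids or psychotropic drugs".

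Section 4.11 gives this among the reasons study treatment ends: "The clinical need for concomitant therapy that is not permitted in the study".

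**The concern.** A permission with caution and a prohibition cannot both apply to one patient taking a benzodiazepine. Whichever section an investigator follows, the other can be breached.

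The first stake is patient safety, on a hazard that section 5.7 itself describes as potentially fatal. The second is trial conduct. Through section 4.11, the choice of section decides whether a patient who needs a benzodiazepine may remain on study treatment. The third, smaller, stake is the analysis: use of such a drug could be counted as a protocol violation under one section and not under the other, which affects who enters the per-protocol population in section 8.3.

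**Working it through.** The main point is a comparison of text.

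| Section | Benzodiazepines | Antidepressants, antipsychotics | Alcohol |
|---|---|---|---|
| 5.7 | allowed with caution | allowed with caution | not allowed |
| 7.1.4 | prohibited | not named | prohibited |
| 4.10, exclusion 15 | not named | admitted after at least 4 weeks of use | not named |
| 7.2.4 | not named; intoxication with hypnotics or psychotropics only | not named; intoxication with psychotropics only | intoxication only |

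1. **Benzodiazepines.** Sections 5.7 and 7.1.4 both name them and give opposite rules. No interpretation is needed to reach the contradiction. Both sections also use CNS depressants as a class term.
2. **Antidepressants and antipsychotics.** Section 5.7 and exclusion 15 agree. Section 7.1.4 conflicts with them only if its undefined category of other CNS depressants is read with the list in 5.7, which classes these drugs as CNS depressants.
3. **Can the text settle it?** Section 7 cannot be set aside as background, because exclusion 15 directs staff to it. No passage ranks the sections, and 5.7 does not cross-refer to 7.1.4. Section 7.1.4 itself opens by calling hypersensitivity the only true contraindication and then states the prohibition.
4. **Lists of disallowed drugs.** Taking 5.7 (alcohol, other opioids), exclusion 15 (capsaicin, NSAIDs, tetrahydrocannabinol, cannabinoids) and the 7.1.4 sentence (benzodiazepines, other CNS depressants, alcohol), benzodiazepines are on 1 of 3, alcohol on 2 of 3, and no drug on all 3.
5. **How many patients.** The documents give no figure. Assuming 1, 2 or 3 users among the 18 evaluable patients of section 8.4: 1/18 = 5.6%, 2/18 = 11.1%, 3/18 = 16.7%. Among the 20 to be enrolled: 5%, 10%, 15%.

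**Minor point (a): buprenorphine units and strengths.** Sections 5.2 to 5.4 state the patch dose per hour. Section 2 has "FDA-approved dose from 5 mcg to 20 mcg/week" and section 5.1 has "transdermal buprenorphine 5 mcg to 20 mcg/week with oral tramadol 50 mg to 400 mg/day". Section 7.1.2 uses mg/h, and the post-radiation step of Table 2 gives 20 mcg with no time unit. Table 1 can be reproduced with the 75:1 ratio from section 5.2:

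- Formula: morphine equivalent in mg/day = dose in mcg/h × 24 × 75 / 1000.
- 5 mcg/h: 5 × 24 × 75 / 1000 = 9 mg. Likewise 10, 15 and 20 mcg/h give 18, 27 and 36 mg. All four match Table 1.
- Read as mcg/week: 5/7 × 75 / 1000 = 0.054 mg/day.
- Read as mg/h: 5 × 24 × 75 = 9,000 mg/day.

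Table 1 is therefore consistent only with mcg/h, and the other units look like drafting errors. Section 7.1.2 also lists three strengths (5, 10, 20), whereas Tables 1 and 2 use 15 as well.

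**Minor point (b): who sees the app scores.** Table 2 adjusts doses through the app when VAS stays above 3/10 for 72 hours, and Study Calendar footnote 5 has the team evaluate the app daily. Section 5.9.4 blinds providers to the scores in a feasibility phase that is not defined. The weekly BPI question 3 covers only the last 24 hours, so it cannot establish a 72-hour trigger.

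**The case against.** The strongest reply accepts the benzodiazepine conflict and disputes its reach.

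- **Scope.** Only benzodiazepines are named in both sections, and exclusion 15 gives antidepressants and antipsychotics a specific rule that agrees with 5.7. This stands for those two classes, where the conflict is conditional. It does not confine the problem to benzodiazepines, because both sections use the class term and 7.1.4 leaves its limits open.
- **The list tally.** The count depends on the passages chosen. Section 5.6 also restricts NSAIDs, Tylenol and CYP3A4 inducers, and 7.1.4 separately advises against use with full opioid agonists. This is fair: the tally shows scattered rules and does not measure harm. The shares of 18 or 20 are likewise only illustrative.
- **Tramadol.** Section 7.2.4 concerns intoxication, so it creates no conflict with prescribed use. That is correct; it matters only because it does not resolve the question.
- **Analysis.** The per-protocol set serves sensitivity analyses only, a major violation is undefined, and the criterion of 10 responders among 18 is untouched. This stands.
- **Safeguards.** The risk is stated openly in 5.7, a history of significant respiratory depression is an exclusion, clinician visits are weekly through week 7, and section 7.1.5 addresses respiratory depression. These reduce harm but do not tell an investigator which rule to follow.
- **Side points.** The post-radiation step refers back to a schedule written in µg/hour. The mg/h figure is an evident slip: a 5 mg patch releasing 5 mg/h would be empty in 5/5 = 1 hour, against the seven days stated. Patient messages and telephone titration (5.1) and symptom-initiated visits (5.9.4) also leave other routes to dose changes. For these reasons both points are rated minor, and no titration delay is claimed.

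**Conclusion.** The concern holds. The protocol gives two incompatible rules on CNS depressants, directly so for benzodiazepines, and contains nothing that reconciles them. For antidepressants and antipsychotics the conflict depends on how the undefined class in 7.1.4 is read.

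The consequence is for safety and conduct: under section 4.11 the same patient could stay on the regimen by one section and come off it by the other. The number of patients affected is unknown, and any share quoted rests on an assumed count. A change in the per-protocol set is possible but inferred. No effect on the primary result is shown. The point must be fixed because the text is wrong as written on a hazard that the protocol itself calls potentially fatal.

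**What to change.** Reconcile sections 5.7, 7.1.4, 7.2.4 and exclusion 15 into one rule on CNS depressants that names the drug classes it covers. Have the eligibility list and section 4.11 point to that rule. The sponsor decides which clinical rule applies.

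As minor edits in the same amendment:

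- Use one buprenorphine dose unit in Section 2, sections 5.1 to 5.4 and section 7.1.2.
- Reconcile the strengths in 7.1.2 with Tables 1 and 2.
- State in 5.4 and 5.9.4 whether the clinicians who titrate see the app scores, and define or remove the feasibility phase.

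The cost is a wording amendment and a memo to staff at the single center, with no new procedures and no additional patients.

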5.8 Monitoring Subject Compliance

Study drug can be dispensed only to eligible patients under the supervision of the investigator or identified sub-investigator(s). The appropriate study personnel will maintain records of study drug receipt through WIPDMP website.

5.9 OM Pain App

5.9.1 Device Description/Overview

The Oral Mucositis (OM) Pain App is a smartphone application that was designed to permit patients to key in pain severity using a visual analog 0–10 scale. The app is programmed with an alarm to prompt the patient to record pain severity at prescribed intervals daily and through spontaneous patient input. Time intervals for prompted pain queries can be customized, when, for instance, patients work a night shift or have specific sleep/wake cycle preferences.

Deidentified data collected on each patient's smartphone will be transferred wirelessly to cloud storage. Data transmitted wirelessly will use HTTP secure (HTTPS) sessions and JSON/XML protocols, such as the security used in online banking. Security measures and only deidentified data will be transmitted. Study participants will be encouraged not to update the smartphone operating system during the conduct of the study. Study PIs and/or study coordinator will perform OM Pain App software updates on smartphones.

Analysis of data collected from smartphones will be performed from cloud-stored data on deidentified sources only. This would be done in collaboration with our co-investigators at University of Wisconsin Milwaukee (UWM). The raw pain scores will be used to generate a time-weighted measure of pain called total area under the pain curve (AUC). Average weekly pain scores will also be calculated. This is a summary measure that integrates serial assessments of a patient's pain over the duration of the study. Architecture of the pain app is illustrated in figures 1 and 2.

5.9.2 Device Distribution to Subjects

The OM Pain App will be installed on the smartphone of each participant. If during the conduct of the study, a smartphone is lost, stolen, or broken, the subject will not be responsible for the cost of the device.

The study is designed for Android platform. However, an iOS app will be developed for the iPhone and will also be tested during this project. See figures 1 and 2 for further illustration and description of architecture, framework, and IT network for mobile platforms.

Deidentified data will be transmitted by wifi to a cloud storage server. Patients who do not have a smartphone will be issued a device with the OM Pain App installed on it at the initiation of their participation in the study. These phones will not have an active cellular phone service; but will have active wifi. Syncing of data from the phone will occur by hardwire connection (during initial testing) or by wifi (later during software testing). The device will be collected from participants at the end of the study period.

5.9.3 Daily Intervention

If enrolled, patients can start using the app up to one week prior to radiation therapy for training and practice. Formal data monitoring would only start once patients start study drug regimen. As noted, subjects will receive a preprogrammed alarm four times a day from their smartphones prompting them to directly enter OM pain levels on the device. Patients may submit as many pain entries as they wish beyond the four minimum levels. The software also allows patients to document self-administration of breakthrough pain medication. This event will prompt immediate entry of a pain level and an automatic pain assessment one-half hour later. Because symptoms of mucositis do not commence typically until the third week of radiation therapy, and no sooner than week 2, we don't expect to start data recording earlier than that. Recording of data will cease five weeks (week 12) after the end of radiation therapy at which time mucositis symptoms typically start to resolve and pain symptoms substantially abate (see the schema).

5.9.4 Avoiding Bias: A viewable graphic summary of pain scores will be a functionality of the app but will be disabled in this study to avoid bias of care provider or participant. For the feasibility phase, patients and providers will be blinded to the pain scores and symptoms will be managed with supportive treatments during routine weekly provider visits and symptom-initiated clinical visits.

5.9.5 Monitoring Compliance: The study coordinator will download data and check the equipment weekly for proper functioning and compliance. Patients will be interviewed weekly to assure the device is functioning correctly and that data are being recorded. Compliance with the device use will be assessed by the percent adherence to the device prompted four times daily pain assessment.

Architecture, Framework, and IT Network for Mobile Platforms

Figure 1 Shows the architecture for the proposed iPhone/Android Apps. To ensure data security and confidentiality, web registration was implemented in the Apps for the web server to generate a unique device ID for the purpose of secure information exchange. The Apps will incorporate an intuitive user interface for recording pain severities in order for the patients to engage in the reporting activities. The reported pain data will be uploaded to a secure web server via secure Hypertext Transfer Protocol (HTTPS) to allow for monitoring by the health professionals.

Figure 2 Shows the general framework for the proposed mobile platforms. The internet-based computing platform consisting of web services, web servers, and database servers will provide web interfaces for professionals and patients as well to monitor the history reports of pain severities.

Figure 1.

Figure 2.

Experimental setup: Our web and data servers will run Windows Server 2008 R2, The Apache HTTP Server, the MySQL Database and the PHP Hypertext Preprocessor (PHP). We will use the Google Android and Apple iPhone platforms running on popular devices such as Apple iPhone, Samsung Galaxy and Motorola Moto X. These cover the majority of app-driven cell phones.

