4. Record of opioid pain medications, laxatives, and antiemetic use from the patient's drug diary will be copied by investigators on weekly clinic visits. This will commence after starting treatment. a) Patients will document pain and supportive medication use data daily in their diaries but that information will be verified and recorded by investigator/research coordinator during weekly clinic visits in the electronic medical record(EMR). This data is currently being collected in a section of pain app. Patients average weekly VAS pain scores (question 3 of BPI questionnaire) will also be documented in EMR during weekly clinic visits as per standard of care and can be used for study purposes.
5. The Oral Mucositis (OM) Pain App will be evaluated by the study team on a daily basis through a real-time pain assessment tool in the mobile app. Patients can start using the OM Pain App before starting therapy to familiarize themselves with the instrument. b) Pain app readings will be recorded up to four times/day. The daily pain data will be analyzed by the UWM research team on a weekly basis.
6. All questionnaires/forms can be recorded on weekly in-person visits from weeks 1–7 then completed weekly through in-person/telephone interviews by CTO staff from week 8–12. Other assessments can also be done over phone during week 8, 10 and 11. Window period of +/-3 days will be allowed for data collection.
7. EKG will be done at screening and then on week 7 and 12 if the patient is on treatment with Buprenorphine patch.
8. Digital photos will be taken to document mucositis on the day of enrollment, treatment initiation, then during week 9 and week 12 clinic visits.

=

LIST OF ABBREVIATIONS

AE	adverse event
ALP	alkaline phosphatase
ALT	alanine aminotransferase
ANC	absolute neutrophil count
AST	aspartate aminotransferase
AUC	area under the curve
BPI	Brief Pain Inventory
BUN	blood urea nitrogen
CBC	complete blood cell (count)
CDK	cyclin-dependent kinases
CQ	chloroquine
CR	complete response
CRC	clinical research coordinator
CRF	case report form
CSF	cerebral spinal fluid
CT	computerized tomography
CTCAE	Common Terminology Criteria for Adverse Events
CTL	cytotoxic T cell
CTO	Clinical Trials Office
DFS	disease-free survival
DLT	dose-limiting toxicity
DSMC	Data and Safety Monitoring Committee
DSMP	data and safety monitoring plan
ER	estrogen receptor
FDA	Food and Drug Administration
GCP	good clinical practice
GVHD	graft-versus-host disease

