5.4 Drug Regimen Titration Schedule

Table 2 Drug Titration Schedule

Drug: Buprenorphine with tramadol for breakthrough pain (**First seven weeks of study**) $T = 0 - 7$ weeks;

Start TD buprenorphine 5 μ g/hour along with oral tramadol 50 mg to 150 mg (total dose over 24 hours) as needed for breakthrough pain when mucositis related pain is $\geq 4/10$ on VAS measured on OM Pain App and BPI. Further dose adjustments will be made through pain app.

- If VAS is $>3/10$ for 72 hours on tramadol 150 mg (total dose over 24 hours) and buprenorphine 5 μ g/hour, then, increase tramadol to 250 mg (total dose over 24 hours).
- If VAS is $>3/10$ for 72 hours, even with tramadol 250 mg (total dose over 24 hours) and buprenorphine 5 μ g/hour, then, increase dose of buprenorphine to 10 μ g/hour.
- If the pain persists VAS $>3/10$ for 72 hours on tramadol 250 mg (total dose over 24 hours) and 10 μ g/hour, then, increase the dose of tramadol to 350 mg (total dose over 24 hours).
- If VAS pain is $>3/10 \times 72$ hours with both tramadol 350 mg (total dose over 24 hours) and buprenorphine 10 μ g/hour, then, increase dose of buprenorphine to 15 μ g/hour.
- If VAS pain $>3/10 \times 72$ hours on tramadol 350 mg (total dose over 24 hours) and 15 μ g/hour of buprenorphine, then, increase the dose of tramadol to 400 mg (total dose over 24 hours) and buprenorphine to 20 μ g/hour.
- If the pain persists and is unbearable at $>3/10$ for 96 hours, despite being on highest dose of both drugs, then, replace tramadol with oxycodone at the clinician's discretion up to 90 mg (total dose over 24-hour period) for pain relief.
- If VAS is $\leq 3/10$ maintained for 72 hours, then, we can start tapering off total daily tramadol dose by 50 mg every day, but not change the buprenorphine dose during the first seven weeks of treatment, as mucosal injury from ongoing radiation may increase pain later.

(Post-radiation period) $T = 8 - 12$ weeks: if necessary, increase dose of buprenorphine up to 20 mcg along with tramadol up to 400 mg/day as per titration schedule used in the first seven weeks until VAS is $\leq 3/10$. If pain is well controlled (VAS $\leq 3/10 \times 72$ hours), start weekly tapering of buprenorphine by 5 mcg and tramadol by 50 mg daily.

Special Circumstances

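### Section 5.9.4 blinds providers to the pain scores that the app-triggered dose steps in Table 2 depend on, and nothing in the protocol reconciles the two

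*Combined protocol and SAP*

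**What the plan says.** **Blinding.** Section 5.9.4 first turns off the app's graphic summary, which "will be disabled in this study to avoid bias of care provider or participant". The next sentence, which opens by limiting itself to a feasibility phase, goes further: "patients and providers will be blinded to the pain scores and symptoms will be managed with supportive treatments during routine weekly provider visits". It ends by adding visits prompted by symptoms.

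**Titration.** Table 2 in Section 5.4 starts treatment when VAS is at least 4/10 on both the app and the BPI, and continues: "Further dose adjustments will be made through pain app". The first escalation is triggered by VAS above 3/10 "for 72 hours on tramadol 150 mg (total dose over 24 hours"), and four more steps use the same 72-hour window. Oxycodone replaces tramadol when VAS stays above 3/10 "for 96 hours, despite being on highest dose of both drugs". Tapering begins when VAS of 3/10 or less is "maintained for 72 hours, then, we can start tapering off total daily tramadol dose by 50 mg every day".

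**Access to scores.** Study calendar footnote 5 says the app "will be evaluated by the study team on a daily basis through a real-time pain assessment tool in the mobile app". The same footnote has the engineering collaborators analyse the data weekly, and Section 5.9.5 has the coordinator download it weekly. The text for Figures 1 and 2 describes professionals monitoring uploaded scores through a web interface.

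**Who titrates.** Section 5.1 gives titration to investigators or sub-investigators by telephone, and asks patients to send a message through the electronic record if their pain stays uncontrolled.

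**The concern.** A provider who is blinded to app scores cannot act on a 72-hour or 96-hour run of app scores. Section 5.1 makes the investigators the titrators, and nobody is named who sees the scores and passes on that a trigger has been met. Two instructions on delivering the tested regimen therefore cannot both be followed.

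Two things are at stake. First, the doses a patient reaches before the week-9 pain score may depend on which instruction the clinic follows, and the protocol gives no basis for choosing. Second, prompt detection of uncontrolled pain depends on the same choice. Section 8.7 justifies having no stopping rule partly by the provision for switching to oxycodone, and in Table 2 that switch is tied to the 96-hour rule.

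**Working it through.** **1. Can each score source feed the Table 2 triggers?**

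| Source | Frequency and span | Shows a 72 h or 96 h run? | Visible to the titrator? |
|---|---|---|---|
| OM Pain App (Sections 5.9.3 to 5.9.5, footnote 5) | Prompted four times a day | Yes | No under 5.9.4; yes under footnote 5 and the text for Figures 1 and 2 |
| BPI item 3 (Section 3.2, Appendix 4) | Weekly; worst pain over 24 hours | No | Yes |
| Patient message, then telephone (Section 5.1) | When the patient reports uncontrolled pain | Not specified | Yes, but no recorded VAS series is required |

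Only the app can supply the runs, and it is the source that 5.9.4 closes to providers. The message route can prompt an increase. It has no counterpart for tapering, because a patient whose pain is controlled is not asked to send a message.

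**2. Does the feasibility-phase qualifier remove the conflict?** The protocol defines no such phase and gives no start or end for one. Sections 3.1 and 8.2 describe the whole trial as testing feasibility. The qualifier cannot be used to exempt any patient.

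**3. Does the conflict touch the stated design?** Section 8.4 gives 18 evaluable patients, success at 10 or more responders, null 0.33, alternative 0.63 and one-sided 5%. By the exact binomial:
- P(X ≥ 10 | n = 18, p = 0.33) = 0.0405
- P(X ≥ 10 | n = 18, p = 0.63) = 0.8165
- 18 / (1 − 0.10) = 20 enrolled

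All three agree with the plan. The conflict does not alter them.

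**4. Illustrative timing.** Table 2 has five escalation steps to the highest doses of both drugs. The slow case assumes one step per weekly visit and no contact in between.
- Table 2 windows: 5 × 3 days = 15 days; with the 96-hour window, 15 + 4 = 19 days to oxycodone
- Slow case: 5 × 7 days = 35 days; one further visit gives 6 × 7 = 42 days
- End of week 9: 9 × 7 = day 63

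| Treatment starts on first day of | Day | Last step, Table 2 windows (+15) | Last step, slow case (+35) |
|---|---|---|---|
| Week 3 | 15 | 30 | 50 |
| Week 4 | 22 | 37 | 57 |
| Week 5 | 29 | 44 | 64 |
| Week 6 | 36 | 51 | 71 |

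For a week-4 start, the oxycodone step falls on day 22 + 19 = 41 under the Table 2 windows and day 22 + 42 = 64 in the slow case. These figures apply only to a patient who fails every step in succession.

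**The case against.** The best defence is that one sentence is out of line. Footnote 5, the text for Figures 1 and 2, and the argument in Section 2.6 for real-time assessment all point to the team seeing the scores. The blinding sentence may be left over from app development, or may have been meant only for the graphic summary. Either is plausible, but neither is stated: the sentence refers to the scores themselves and follows a separate one about the graph. An arrangement in which a coordinator sees the scores and reports only that a trigger has been met would also reconcile the texts, but none is described.

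A reader might infer that the dosing algorithm cannot run at all. The documents do not support that. Section 5.1 lets patients report uncontrolled pain and investigators titrate by telephone, and 5.9.4 itself allows visits prompted by symptoms. The conflict is confined to the app-triggered steps.

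A reader might also infer that many patients would be under-titrated at week 9, so that a negative result could not be attributed to the regimen. That does not follow either. No passage prescribes one step per weekly visit, and no passage says how many patients would need all five steps. The figure of around 20 percent in Section 5.1 concerns inadequate control on the highest buprenorphine dose, which is a different quantity. Sections 3.2 and 5.1 expect most patients to start by week 4, and even in the slow case a patient starting on day 22 reaches the last step on day 57, before day 63. The week-5 case misses by one day, inside the calendar's ±3-day window. Only the week-6 start clearly misses.

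**Conclusion.** The contradiction is real and should be corrected. The blinding sentence in Section 5.9.4 and the app-triggered steps of Table 2 cannot both be followed. The weekly BPI cannot take the app's place, and the message-and-telephone route covers only part of what Table 2 requires. Delivery of the regimen before the week-9 endpoint, and prompt detection of uncontrolled pain, depend on which text governs.

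The effect on the result cannot be sized from the documents. The contrast of 35 days with 15 illustrates a slow case under a stated assumption; it does not forecast what the clinic would do. The number of patients affected is unknown. Sample size, significance level and power stand as stated. The documents also do not settle which text was intended, and this review takes no position on that.

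**What to change.** Reconcile study calendar footnote 5, Section 5.1, Table 2, Sections 5.9.4 and 5.9.5, and the text for Figures 1 and 2. State in one place, and cross-refer from the others:

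1. who sees app scores, by role, and how often;
2. which score, app or BPI, feeds each Table 2 trigger (start, 72 hours, 96 hours, taper);
3. how the message-and-telephone route relates to those triggers, and what VAS record supports a dose change made through it;
4. what, if anything, Section 5.9.4 still blinds, for whom, and what the feasibility phase is.

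This asks only that the passages agree. Which clinical text should prevail is for the investigators, and no dose or titration rule is proposed. The cost is a wording amendment, which needs IRB approval under Section 10.5.3. The endpoint, test and sample size do not change.
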